3.1 Patient Disposition

The following tables will be provided:

- The number of subjects per analysis population and study site (frequency statistics) •
- The number of subjects by treatment group and overall •
- The number of subjects by study visit, treatment group and overall (frequency statistics) •
- The number of major protocol deviations by treatment group and overall (Final Analysis only) •

The following listings will be provided:

- Analysis population details (incl. reason not in analysis population) •
- Attended study visits (incl. planned date and actual date) .
- Protocol deviations (Final Analysis only) •

3.2 Screening Failures and Drop-Outs

Following tables will be provided:

- The number of screening failures (frequency statistics) •
- Early terminations by treatment group and overall (frequency statistics) •
- Reason for early termination by treatment group and overall (frequency statistics) •

The following listings will be provided:

- Screening failure with reason •
- Early terminations with reason

Page 22 of 47

4. BASELINE EVALUATION

Treatment groups were defined in section 2.3. For the Preliminary Analysis baseline evaluation tables will be produced for the mITT population. In the Final Analysis the tables will be repeated for the PP population.

4.1 Demographic Aspects

The following tables / listing will be provided:

- Age (calculated as difference in years between year of birth and year of informed consent) will be tabulated by treatment group and overall (summary statistics).
- Gender by treatment group and overall (frequency statistics)
- Ethnicity will be tabulated by treatment group and overall (frequency statistics)
- A data listing of all demographic data will be prepared (subject number, treatment group, date of birth, date of informed consent, age, gender and ethnicity).

4.2 Physical Examination

The following tables / listing will be provided:

- The results (normal / abnormal / not done) of the physical examination of ten body systems at screening will be tabulated by body system ("General appearance and skin", "Head/Eyes/Ears/Nose/Throat", "Cardiovascular System", "Respiratory System", "Abdominal and Gastrointestinal System", "Musculoskeletal System", "Neurological System", "Lymph nodes", "Other")
- A data listing of physical examinations at screening (including description of abnormal findings) will be prepared.

4.3 Vital Signs

The following tables / listing will be provided:

- Blood pressure (systolic and diastolic, in mmHg), pulse rate (in beats/min) and body temperature (in °C) and at baseline will be tabulated by treatment group and overall (summary statistics).
- A data listing of vital signs (patient number, treatment group, date of assessment, blood pressure systolic, blood pressure diastolic, pulse rate, body temperature) will be prepared.

4.4 Virology

A data listing of virology details (patient number, treatment group, sampling date, test parameter, result) will be prepared.

4.5 Pregnancy Test

A data listing of pregnancy test details at screening (patient number, treatment group, pregnancy test performed: yes/no/not applicable, date, result) will be prepared.

4.6 Medical History

Medical history entries will be coded using the Medical Dictionary for Regulatory Activities (MedDRA, cp. section 2.15). The version which will actually be used will also be indicated in the respective tables and listing. The following tables / listings will be provided:

- The number and proportion of subjects with at least one medical history entry as well as the total number of medical history entries will be tabulated.
- Additionally, the number and proportion of subjects with at least one medical history entry will be • tabulated by System Organ Class (SOC) and Preferred Term (PT) (frequency statistics). The table will be sorted by relative frequency of SOCs and by relative frequency of PTs within SOCs.
- A data listing will be provided for all medical history entries.

4.7 Vaccination History

Vaccination history covers the last three years prior to screening. A data listing of vaccination history details will be provided.

4.8 Prior and Concomitant Medications

All medications entered in the concomitant medication-log of the eCRF will be coded using the WHO Dictionary (cp. section 2.15).

Medications stopped clearly prior (<) to the date of first study treatment will be considered prior medication, all other medications are considered to be concomitant. Medications with a missing stop date or an incomplete stop date where it cannot clearly be decided if the stop date was before or after the date of first study treatment or if "currently ongoing", "ongoing at final examination" or "dosage changed" is ticked will be considered concomitant. The following tables/listings will be provided:

- The number and proportion of subjects with at least one concomitant medication as well as the total • number of concomitant medications will be tabulated.
- Additionally, the number and proportion of subjects with at least one concomitant medication will be tabulated by ATC level 2. The table will be sorted by relative frequency of ATC level 2.
- A data listing will be provided for all prior medications (incl. medication, ATC level 2, start date, stop date, . dose/unit/frequency, route of administration, indication)
- A data listing will be provided for all concomitant medications (incl. medication, ATC level 2, start date, • stop date, ongoing, dose/unit/frequency, route of administration, indication)

5. EFFICACY ANALYSIS

Not applicable for this study.

6. IMMUNOGENICITY ANALYSIS

Immunogenicity analysis will be presented for the mITT and PP population for the Final Analysis, whereas the Preliminary Analysis is presented for the mITT population only. Analysis are stratified by treatment group (defined in subsection 2.3) and overall.

For statistics in tables only actual numbers can be used. Therefore the following substitution rules will apply:

Actual PRNT ₅₀ value (used for listings)	Derived $PRNT_{50}$ value used for tables
Number (greater or equal 10)	number (greater or equal 10)
"< 10"	5
"> 1280"	1280
"MISSING"	missing

Actual ELISA (CHIK) value (used for listings)	Derived ELISA (CHIK) value used for tables
Number (greater or equal 2)	number (greater or equal 2)
"< 2"	1
"MISSING"	missing

Actual ELISA (Measles) value (used for listings)	Derived ELISA (Measles) value used for tables
Number (greater or equal 50)	number (greater or equal 50)
"< 50"	25
"> 5000"	5000
"MISSING"	missing

Seroconversion rates (PRNT_SC) will be calculated as follows:

- Case 1: If $PRNT_{50}$ value \geq 10, then seroconversion $PRNT_SC$ is set to "YES",
- Case 2: If PRNT₅₀ value< 10, then seroconversion PRNT_SC is set to "NO".
- Case 3: If the PRNT₅₀ value is missing then seroconversion PRNT_SC is set to "missing"
- Case 4: If PRNT₅₀ is "> 1280", then seroconversion PRNT_SC is set to "YES".

Seroconversion rates (ELISA_SC) will be calculated as follows:

- Case 1: If ELISA (CHIK) value ≥ 16, then seroconversion ELISA_SC is set to "YES",
- Case 2: If ELISA (CHIK) value < 16, then seroconversion ELISA_SC is set to "NO".
- Case 3: If the ELISA (CHIK) value is missing then seroconversion ELISA_SC is set to "missing"

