***Immunogenicity Analysis:***

The vaccine immunogenicity was determined by the presence and quantity of functional Chikungunya virus neutralizing antibodies in the sera of vaccinated subjects. The neutralization titers were determined by 50% plaque reduction neutralization test (PRNT50) and total antibody levels were determined by hemagglutination inhibition assays (HIA).

The primary end-point of the study, which was immunogenicity on day 28 after the first vaccination, showed that a single MV-CHIK immunization elicits functional antibodies in all treatment cohorts. The medium and high dose groups induced similar levels of neutralizing antibodies, which were significantly higher than the low dose group and the Priorix control groups. A second immunization at one or three months interval boosted the titers in all treatment groups clearly, figure 2). The low dose group showed relatively low titers of both functional and total antibody levels. A second immunization did boost the titers clearly, however, this dose level is not suitable for a single shot vaccine. The medium dose group elicited significantly higher titers after one or two immunizations. The highest functional and total anti-CHIKV titers were elicited in the highest dose group. The functional antibodies were persistent over the study period. Very similar results were obtained by HAI. Total antibody levels have been induced by a single immunization, and boosted by a second dose.

The Measles antibody titers as measured by ELISA were boosted in all treatment groups (MV-CHIK and Priorix®) after the first vaccination. No clear trend between the individual groups was visible but an increase in Measles virus dose increased the geometric mean titer (GMT). The measles ELISA titers that were induced after the first immunization were close to the detection limit of the assay. Therefore, a not additive effect was visible after a second immunization.

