### 13.1 Immunogenicity Analysis

The primary immunogenicity analysis will compare the anti-chikungunya PRNT50 antibody geometric mean titer (GMT) 28 days after one or two immunizations in the Per Protocol (PP) analysis population between the treatment groups. GMTs and GMT ratios will be estimated by applying an analysis of variance including the factor vaccination group. This will be done using log-10 transformed data and taking the anti-log of the resulting point estimates for the least squares means, least squares means differences and the corresponding 2-sided 95% CIs. P-values will also be provided to compare GMTs for the MV-CHIK groups (pairwise comparisons adjusted for multiple comparisons according to Tukey-Kramer; groups A vs. B, C vs. D, M1 vs. M2), e.g. 28 days after the 2nd MV-CHIK dose, etc. Likewise, SCRs will also be compared between groups. Seroconversion will be defined as anti-Chikungunya PRNT50 titers  $\geq 10$ .

Measles ELISA titers will be analyzed as described above. In addition, the effect of pre-existing anti-measles immunity will be assessed: The CHIKV PRNT50 titers 28 days after first vaccination, between the four baseline measles titer groups, defined by baseline percentiles

(25%, 25-50%, 50-75%, 75-100%), will be compared. No stratification by dose groups is intended.

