### 13.4 Sample Size Justification

No formal sample size calculation has been performed for this phase 2 trial, but the sample size is typical for phase 2 trials, and in our experience, has been useful to assess the immunogenicity of vaccines.

Results of the predecessor study MV-CHIK-101 allow to assess the usefulness of the chosen sample size:

In phase I study MV-CHIK-101, a GMT of 7.3 (LOG10 SD 0.254) at day 28 in the placebo group and a GMT 13.7 (LOG10 SD 0.515) in the lowest dose group (MV-CHIK 0.05 mL = 1.5 x10^4 TCID50) was observed. Both higher dose groups (MV-CHIK 0.25 mL = 7.5 x10^4 TCID50; 1 mL = 3 x10^5 TCID50) demonstrated higher GMTs of 48 (LOG10 SD 0.466) and 45.7 (LOG10 SD 0.579).

In the present phase II study, the sample size of 60 subjects in the MV-CHIK dose group vs. 10 subjects in the corresponding control group within each dose group A-D will allow for a detection of a GMT of 15.4 (MV-CHIK) vs. 7.3 (placebo) with a LOG10 SD of 0.6 vs. 0.26 and statistical power of 80% (two-sided alpha=5%, unequal-variance t-test). Between dose groups, the sample size of 60 subjects per group will allow for a comparison of a GMT of 45.7 vs. 22.4 (LOG10 SD 0.6 for both groups) with a statistical power of 80% (two-sided alpha=5%, equal-variance t-test).

Since the magnitude of GMTs and LG10 DS in this assessment is comparable to the observed results in study MV-CHIK-101, and the statistical methodology applied in the current study has a higher statistical power than pairwise t-tests, the chosen sample size seems adequate.

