2.7 Inferential Analyses

Inferential analysis on immunogenicity endpoints will only be performed on the PP and ITT population. The significance level will be 0.05. All p-values will be two-sided and rounded to four decimal places.

GMTs and GMT ratios will be estimated by applying an analysis of variance (ANOVA) by using log-10 transformed data and taking the anti-log of the resulting point estimates for the least squares means, least squares means differences and the corresponding 2-sided 95% Cls. Pairwise comparisons for multiple comparisons will be adjusted according to Tukey-Kramer. For the definition of the baseline percentiles treatment groups A, B, C and D will be used.

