6.4 Measles Antibodies Assessment

Measles antibody titers are taken at, at Visit 1 (Day 0), Visit 2 (Day 28), Visit 3 (Day 56), and for M1 and M2 additionally at Visit 0 (Day -28) and ET visit if applicable.

Following tables/listing will be provided for the Preliminary and Final Analysis:

- The number of measles antibody titer samples drawn (yes/no) will be tabulated by visit, treatment group and overall (frequency statistics).
- The geometric mean titer (GMT) for the variable measles antibodies by ELISA will be tabulated by visit, treatment group and overall (summary statistics).
- A data listing of measles antibody results will be provided by visits.

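### Measles ELISA titres above 5000 are analysed as exactly 5000, with no count or censored analysis, although Phase 1 titres were near the assay limit; for PRNT50 the same rule needs only a sensitivity check.

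*SAP*

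**What the plan says.** SAP section 6 introduces its coding with "For statistics in tables only actual numbers can be used. Therefore the following substitution rules will apply". For measles ELISA, results below 50 become 25 and results above 5000 become 5000. For PRNT50, results below 10 become 5 and results above 1280 become 1280. Listings keep the reported value. SAP 2.7 then runs the ANOVA on log10 data, "taking the anti-log of the resulting point estimates for the least squares means, least squares means differences".

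Protocol 2.4 says of Phase 1: "The measles ELISA titers that were induced after the first immunization were close to the detection limit of the assay". The next sentence draws the consequence: "Therefore, a not additive effect was visible after a second immunization".

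The documents differ on how measles titres are handled. Protocol 13.1, after setting out GMTs, ratios and confidence intervals for PRNT50, says "Measles ELISA titers will be analyzed as described above". SAP 6.4 gives summary statistics only: "The geometric mean titer (GMT) for the variable measles antibodies by ELISA will be tabulated by visit". SAP 2.7.2 lists no ANOVA of measles titres as an outcome.

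Neither document plans a retest at higher dilution, a count of values above the limit, or an analysis that treats them as censored.

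**The concern.** A titre reported as above 5000 is known only to lie somewhere beyond 5000. Coding it as 5000 lowers the GMT of any group with such values and compresses the spread. The protocol itself attributes a missing second-dose measles effect in Phase 1 to the assay limit. Titres there had just been boosted in all groups, so the upper limit must be meant.

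This trial again gives two measles-vector doses, at up to 5x10^5 TCID50 against a Phase 1 maximum of 3x10^5. M1 and M2 also receive an MMR vaccine on Day -28. Anti-measles antibody is a secondary endpoint, and immunogenicity under recently boosted measles immunity is another. The Day -28 and Day 0 measles titres show how large that boost was. If many Day 0 values are capped, the boost is understated, and a finding of little further rise could be partly an effect of the coding.

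**Working it through.** **Inputs from the documents.** Caps of 5000 and 1280, and the PRNT50 floor (below 10 coded as 5): SAP 6. PRNT50 planning values of GMT 45.7 against 22.4, log10 SD 0.6, 60 per group: Protocol 13.4. Phase 1 Day 28 PRNT50 GMTs of 48 (SD 0.466) and 45.7 (SD 0.579) in the two higher dose groups: Protocol 13.4.

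**Assumed, because the documents give no values.** Measles GMTs and SDs after vaccination, and PRNT50 GMTs after two doses. Titres are taken as log-normal.

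**Plan's own figure.** Protocol 13.4 states the between-dose comparison "with a statistical power of 80% (two-sided alpha=5%, equal-variance t-test". The log10 difference is log10(45.7/22.4) = 0.310, and the non-centrality is 0.310 / (0.6 × √(2/60)) = 2.83. With 118 degrees of freedom the power is 80.1%, so the figure reproduces (80.7% by the normal approximation used below).

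**Formula.** For log10 titre with mean μ and SD σ, limit c on the log10 scale, and z = (c − μ)/σ:

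- share above the limit = 1 − Φ(z)
- mean of the coded value = μΦ(z) − σφ(z) + c(1 − Φ(z))

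The reported ratio is 10 to the power of the difference in coded means.

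**Measles, worked case.** GMT 2500 against 1250, SD 0.4, c = log10 5000 = 3.6990.

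- Higher group: μ = 3.3979, z = 0.753, 22.6% above 5000. Coded mean = 3.3979 × 0.7741 − 0.4 × 0.3006 + 3.6990 × 0.2259 = 3.3457, a GMT of 2217.
- Lower group: μ = 3.0969, z = 1.505, 6.6% above 5000. Coded mean = 3.0853, a GMT of 1217.
- Reported ratio: 2217/1217 = 1.82 instead of 2.

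**Measles, range** (true ratio 2; the GMT named is the higher group's):

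| Higher GMT | SD | Above 5000 | Reported ratio |
|---|---|---|---|
| 1000 | 0.3 to 0.5 | 1% to 8% | 2.00 to 1.94 |
| 2500 | 0.4 | 23% | 1.82 |
| 3000 | 0.3 to 0.5 | 23% to 33% | 1.84 to 1.70 |
| 5000 | 0.4 | 50% | 1.56 |
| 5000 | 0.3 to 0.5 | 50% | 1.61 to 1.53 |

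The same figures apply to a rise within one group, such as Day -28 to Day 0, if the SD is the same at both visits. At GMT 5000 and SD 0.4 the coded SD falls to 0.23, so an interval would be narrow around a biased value.

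**Unequal spread.** With true GMTs of 4000 in both groups but SD 0.5 against 0.25, the coded GMTs are 2801 and 3494. The ratio is 0.80 where no difference exists.

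**PRNT50 at the documented values.** For 45.7 against 22.4 with SD 0.6, 0.8% and 0.2% exceed 1280. The cap alone moves the ratio from 2.040 to 2.034. The floor alone gives 1.951, so the lower substitution does more. At the Phase 1 values of 48 and 45.7 with their own SDs, 0.1% and 0.6% exceed the cap.

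**PRNT50 at assumed higher GMTs** (SD 0.6, true ratio 2.04, cap only; uncapped power 80.7% at 60 per group, unadjusted):

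| Higher GMT | Above 1280 | Reported ratio | Power |
|---|---|---|---|
| 200 | 9% | 1.96 | 80.3% |
| 400 | 20% | 1.85 | 79.0% |
| 800 | 37% | 1.67 | 75.7% |

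**Does a censored model recover the ratio?** In 400 simulated trials per case, with a true measles ratio of 2, substitution gave 1.74 and the censored model 2.02 at 4000 against 2000 (SD 0.3). At 5000 against 2500 (SD 0.5) they gave 1.52 and 1.96.

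**The case against.** A reader might infer three stronger points, none of which the documents support.

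- *The Phase 1 assay hit its ceiling, and that ceiling was 5000.* Protocol 2.4 says only that titres were close to the limit. It gives no number and no share of subjects, and does not say that this trial uses the same assay. It also reports that measles GMT rose with dose, so a dose trend remained visible.
- *The primary PRNT50 comparison is materially biased.* The only PRNT50 GMTs given are 48 or lower, where the cap does almost nothing. Protocol 2.4 says that a second dose clearly boosted titres but gives no two-dose figure. Even at an assumed GMT of 800, power falls only from 80.7% to 75.7%.
- *The bias always runs towards no difference.* That needs similar spreads; with unequal spreads the cap can create a difference.

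Other defences also have force. The SAP tabulates measles GMTs without ratios. Its vector-immunity analysis uses Day 0 quartiles of groups A to D, which an upper cap does not alter unless more than a quarter of baseline values exceed 5000. Seroconversion is unaffected, and counts above the limit can be recovered from the listings. Replacing the primary PRNT50 estimator would be hard to justify: many control and M2 values at Day 56 should sit at the floor, where a log-normal model with common spread fits poorly.

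What these defences do not answer is that the tabulated measles GMTs are lowered by any capped value, that the protocol itself names the assay limit as a Phase 1 problem, and that the plan has no provision for it.

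**Conclusion.** The concern holds for measles ELISA as a real risk of unknown size. Any value above 5000 lowers the tabulated GMT. If post-vaccination GMTs are about 1000, the effect is small; at 2500 to 5000 a true two-fold ratio or rise would show as roughly 1.8 to 1.6 (SD 0.4). These GMTs and SDs are assumptions, and the ratios also assume log-normal titres with similar spread.

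For PRNT50 the documented figures show a negligible effect. The cap would matter only if two-dose GMTs reached several hundred, which the documents neither show nor exclude. The primary analysis need not be replaced.

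**What to change.** In SAP 6:

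1. For measles ELISA and PRNT50, report the number of values above and below each assay limit by group and visit.
2. Analyse measles titres with a log-normal censored model using the same group factor (for example SAS PROC LIFEREG), and present its GMTs beside the substituted ones. Reconcile Protocol 13.1 with SAP 6.4 on whether measles ratios are reported; if they are, give them from both analyses.
3. Keep the substituted ANOVA as the primary PRNT50 analysis. Add the censored model as a sensitivity analysis, treating both results below 10 and results above 1280 as censored.

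The cost is SAP wording, one more SAS procedure and a few tables, with no new data. The downside is that the model assumes log-normal titres and fits poorly in groups lying mostly at the floor, so its estimates there should be read with the counts.

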6.1 Primary Endpoint

The primary immunogenicity endpoint is the immunogenicity on Day 56 in the mITT population confirmed by the presence of functional antibodies as determined by the plaque reduction neutralization test (PRNT₅₀).

Following tables will be provided:

SAP (MV-CHIK-202, FINAL 3.0, 09-May-2018) Based on: STAT03_A Statistical Analysis Plan Version 5.0, Effective Date 16-Dec-2016 Confidential and intellectual property of Assign DMB. Page 26 of 47

Confidential and intellectual property of Assign DMB. No part of this document or its contents may be duplicated, referenced, published or otherwise disclosed in any form or by any means without prior written consent of Assign DMB.

- Number of functional antibodies blood samples drawn (yes/no) will be tabulated by treatment group and overall (frequency statistics).
- The geometric mean titer (GMT) of the functional antibodies by PRNT₅₀ will be tabulated by treatment group and overall (summary statistics).

Statistical analysis will be performed as described in section 2.7.1.

